intake of 450 kcal / day compared to approximately 250 kcal / day in the other two groups. The results showed that with intensive changes in lifestyle, the risk of DM2 was reduced by 58%, and with metformin by 31%; even so, the cumulative incidence of DM2 in 3 years was 14.4% in the intervention group, 21.7% in the metformin group, and 28.9 in the placebo group [71]. However, the long-term results (15 years) this intervention showed that the effect of the treatment is lost over time and that eventually the majority of patients will develop DM2.

In addition to metformin, other antidiabetic medications have been used: acarbose in a cohort of 1429 patients with ITG showed a reduction in DM2 risk of 25% with a necessary number to treat of 11 to avoid a case of DM2, however, more of the fourth part of patients did not complete the follow-up due to the side effects of the medication [72]; rosiglitazone in the DREAM study that included 5269 patients with GAA and / or ITG randomized to 4-8mg of rosiglitazone or placebo, at an average follow-up of 3 years, the rosiglitazone-treated group showed a DM2 risk reduction of 62% [73 ]; The ACT NOW study that used pioglitazone 45mg daily in subjects with GAA and / or ITG shows a risk reduction of DM2 of about 80% compared to placebo [74].

Currently, the pharmacological interventions used in patients with DM2, are directed towards pathophysiological alterations, that is, much emphasis has been made recently so that the treatment is implemented with a pathophysiology-based approach. In prediabetes, if we try to prevent the progression of the disease, it is clear that the options that may have a major impact on each of the pathophysiological alterations are those that could have the greatest effect to prevent the progression of the disease [26, 27, 43, 46, 75]; Within these pharmacological interventions, those that could be more effective, due to the pharmacological profile, are:

- **METFORMIN:** Metformin is the most widely used antidiabetic drug in the world. Although its main effect is exerted at the liver level, it also has an effect on other tissues such as muscle, adipose and pancreatic tissue, therefore its effects are related to the control of insulin resistance and / or pancreatic insulin secretion. At the liver level, metformin activates an enzyme known as AMP kinase (AMPK), which causes an

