have an important role in the disease. There are two incretins, GLP-1 and GIP, of these two, the first is the one that has been reduced in patients with DM2 and with prediabetes [34, 35, 47, 80] and both are produced and released by intestinal cells. The pharmacological effects of incretins are: increased insulin secretion, decreased glucagon secretion, delayed gastric emptying, reduced appetite which leads to weight reduction. In general there are two ways to increase the incretin effect, by applying incretin analogs, which are injectable, and by inhibiting the enzyme that degrades the endogenous GLP-1, which is dipeptidyl peptidase 4. When found to be reduced the incretin effect in patients with DM2 and with prediabetes, and knowing that the effect of incretinomimetic drugs improves the function of the pancreatic islet and could have some effect on the peripheral action of insulin [81-84], it is interesting to know the impact that they could have on DM2 prevention, especially when combined with insulin sensitizers. There are few studies that evaluate the effect of incretins in people with prediabetes; With GLP-1 analogues, a study randomized 38 patients with GAD or IDDM to receive exenatide 10 µg every 12 hrs subcutaneously for 24 weeks, finding that in addition to the weight-reducing effect, a large percentage of patients with prediabetes treated with exenatide reverted to normal (77% vs. 56% for the placebo group) [85]. In another randomized clinical trial, the effect of liraglutide, another analog of GLP-1, on glucose metabolism, insulin resistance and insulin secretion in 24 patients treated with liraglutide and 27 with placebo, of which 10 and 11 were compared, respectively, had impaired fasting glucose + glucose intolerance; a 29% reduction in peripheral insulin resistance was achieved and a 21% increase in insulin secretion [86]. In another study, 22 patients with GAD were randomized to receive 100 mg of sitagliptin, DPP-IV inhibitor, for 8 weeks reporting no effect on glucose metabolism, although reports of some clinical cases mention an important effect on glucose in patients with prediabetes. Other non-antidiabetic medications have also been used and have shown variable results on the prevention of DM2 (valsartan, statins, orlistat, fibrates, estrogens, etc.) [87].

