### **MATERIAL AND METHODS**

**Type of study:** Single Center Parallel Clinical trial, randomized, double blind

**Study universe:** Mexican patients with mixed prediabetes and obesity.

**Study population:** Mexican patients with mixed prediabetes and obesity, from the State of Guanajuato.

**Location:** Regional High Specialty Hospital of Bajío and Division of Health Sciences of the University of Guanajuato, León, Gto.

**Type of sampling:** Non-probabilistic, of consecutive cases.

**Sample size:** The sample size calculation was performed based on the formula to compare proportions. We expect that quadruple therapy (linagliptin + empagliflozin + metformin + lifestyle modifications), improve at least 75% the outcome variables (insulin resistance, pancreatic islet function and cardiovascular function), at 6 months of initiated the intervention, as long as the standard therapy (metformin + lifestyle modifications) achieves only 30% [69-71, 73], so that the study is designed to detect a minimum difference of 45% between the study groups with a type I (alpha) error of 0.05 and a sample power of 80%, and according to the following formula [108]:

$$n = \frac{(Z_{\alpha/2} + Z_{\beta})^2 p_1(1-p_1)(r + 1)}{(d)^2 r}$$

Where,

$$(Z_{\alpha / 2} + Z_{\beta})^2 = 7.9$$

p1 = proportion of individuals in the best treatment who did not achieve improvement = 0.25

p2 = proportion of individuals in the worst treatment who did not achieve improvement = 0.70

r = ratio of individuals in the treatment groups = 1

d = difference expected to be found = 0.45

n = 14 + 20% of losses = 17 patients per group

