### **Intervention and follow-up**

All patients will receive nutritional guidance, meal plan and physical activation recommendations during the study at the Metabolism Research Laboratory of the University of Guanajuato and/or at the Metabolic Unit from the Hospital Regional de Alta Especialidad del Bajío. All patients will have a monthly follow-up with fasting glucose measurement, anthropometry, global clinical evaluation and adherence to treatment (by counting pills consumed monthly by the patient).

Adherence to drug treatment: Information about the disease, its possible complications, the purpose of the treatment to be followed, the exact dose, frequency of administration and duration of therapy, as well as the therapy will be transmitted in an adequate and understandable way to the patient. The consequences of not receiving it. The patient will be suggested to develop a plan as complex as possible and adapted to medications, doses and schedules with daily acts. Sort your medications by time sector (morning and night) and keep them in a visible place.

Nutritional treatment: a feeding plan will be given to each patient, with the aim of achieving a 7% weight loss during treatment. The total energy contribution must be adapted in order to maintain a recommended weight. The energy intake will be between 25 - 30 Kcal / kg/day. The recommended composition of the dietary regimen as follows: total fat 25 -30%, saturated fat <10%, with a predominance of monounsaturated (up to 15%); carbohydrates 50% -60 %; protein 15 – 20 % (1.2 g / body weight (kg) / day). Initially it is recommended to reduce the usual consumption 250 to 500 kcal / day. To determine the adherence to the dietary regimen , the food records of two days of the week and one day of the weekend, and the food consumption frequency questionnaire.

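### The 30% control rate has no shown source, and the stated 80% power is about 66–68% at the planned 14 evaluable patients per arm

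*Combined protocol and SAP*

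**What the plan says.** The Sample size paragraph (Combined protocol and SAP, MATERIAL AND METHODS) compares proportions at 6 months. It expects at least 75% improvement on quadruple therapy in insulin resistance, islet function and cardiovascular function, "as long as the standard therapy (metformin + lifestyle modifications) achieves only 30% [69-71, 73"]. It then sets a minimum difference of 45 points "with a type I (alpha) error of 0.05 and a sample power of 80"%.

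The inputs are given as non-response: "p1 = proportion of individuals in the best treatment who did not achieve improvement = 0.25" and "p2 = proportion of individuals in the worst treatment who did not achieve improvement = 0.70". The squared sum of the two normal deviates is taken as 7.9 and allocation is 1:1. The result is 14 per group, or 17 with 20% added for losses.

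The cited trials are described under TREATMENT OF PREDIABETES. For the large lifestyle-and-metformin prevention trial, for example, the text says that "with intensive changes in lifestyle, the risk of DM2 was reduced by 58%, and with metformin by 31"%.

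**The concern.** A two-proportion calculation needs the proportion of patients in each arm who meet a response definition. A relative reduction in the incidence of diabetes is a ratio of two risks and cannot be entered in its place. If the citations supply only such ratios, the control rate is an assumption presented as evidence.

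Separately, the printed formula contains one arm's variance, so the 80% needs checking even if 75% and 30% are accepted. The statistical analysis section plans tests at p<0.05 and mentions no confidence intervals, so a reader would use the stated power to judge what a non-significant result means.

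**Working it through.** **1. What the cited trials supply.** As described in the background section:

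| Cited trial | Figure given |
|---|---|
| Diet and exercise trial [69] | risk of diabetes reduced by 33% (diet), 47% (exercise), 38% (both) |
| Finnish lifestyle trial [70] | reduced by 58% |
| Lifestyle and metformin prevention trial [71] | reduced by 58% (intensive lifestyle) and 31% (metformin with routine annual advice); 3-year cumulative incidence 14.4%, 21.7% and 28.9% (lifestyle, metformin, placebo) |
| Rosiglitazone trial [73] | reduced by 62% |

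None is a proportion improving in insulin resistance, islet function or cardiovascular function, at 6 months or at any other time. The figures nearest to 30% are 31% and 33%, but the sample-size paragraph does not say that either was used.

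**2. Reproducing the plan's sample size.** With p1 = 0.25, d = 0.45, r = 1:

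n = 7.9 × 0.25 × 0.75 × 2 / 0.45² = 2.9625 / 0.2025 = 14.63, printed as 14. Then 14 × 1.2 = 16.8, so 17. Losing 20% of 17 leaves 13.6, about 14 evaluable.

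**3. Both arms' variances.** The printed formula never uses p2(1−p2) = 0.70 × 0.30 = 0.21, which is larger than p1(1−p1) = 0.1875.

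- Unpooled: 7.9 × (0.1875 + 0.21) / 0.2025 = 15.5, so 16 per arm.
- Standard two-sided formula, with pooled variance under the null as the chi-square uses: [1.96 × √(2 × 0.475 × 0.525) + 0.8416 × √0.3975]² / 0.2025 = 18.1, so 19 per arm.

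**4. Power at the plan's own rates (75% versus 30%).** Normal approximation: Φ{[d√n − 1.96 × √(2 × 0.525 × 0.475)] / √0.3975}, where the two roots are 0.706 and 0.630.

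- n = 14: (1.684 − 1.384) / 0.630 = 0.475, power 68%.
- n = 17: (1.855 − 1.384) / 0.630 = 0.747, power 77%.

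Exact power comes from summing the binomial probabilities of all outcome pairs that give p<0.05:

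| Evaluable per arm | Uncorrected chi-square | Fisher | Normal approximation |
|---|---|---|---|
| 14 | 66% | 52% | 68% |
| 17 | 80% | 68% | 77% |

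Rounding 14.63 up to 15 would raise the normal-approximation figure only to 72%, so most of the shortfall comes from the single-arm variance.

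**5. Sensitivity to the control rate.** The document's reversion figures outside active-drug arms are 25% over 3–5 years as natural history (prediabetes section) and 56% on placebo at 24 weeks (exenatide trial, "77% vs. 56% for the placebo group"). Both come from other populations and another outcome, so they serve only as a range. Exact uncorrected chi-square:

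| Quadruple | Control | Difference (points) | Power, 14 per arm | Power, 17 per arm |
|---|---|---|---|---|
| 75% | 25% | 50 | 76% | 88% |
| 75% | 30% | 45 | 66% | 80% |
| 75% | 40% | 35 | 45% | 58% |
| 75% | 56% | 19 | 18% | 21% |
| 85% | 40% | 45 | 72% | 81% |

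The last row keeps the 45-point difference. The fall in the rows above it therefore comes from a smaller assumed difference, not from a higher control rate as such.

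**The case against.** A reader might infer that 30% is simply the 31% metformin result, that the protocol's own figures contradict it, and that the true control rate is nearer 58%. The control arm receives metformin plus a feeding plan "with the aim of achieving a 7% weight loss during treatment" and a recommendation of 150 minutes of exercise a week, which are the targets of the intensive lifestyle arm. The documents do not support that reading, for these reasons:

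- The paragraph does not identify the figure behind 30%, and 33% for diet is also close. The 31% arm was not metformin alone, since it also had routine lifestyle advice.
- The 58% is a relative risk reduction, so it cannot bound a response proportion. It also came from a programme with 16 personalised sessions in 24 weeks, whereas this plan offers recommendations with monthly follow-up.
- The 56% on placebo is reversion to normal in a differently selected population. This trial requires both impaired fasting glucose and glucose intolerance, and the protocol counts patients with both, plus overweight and other risk factors, among the most likely to progress. The 25% natural-history figure points the other way.
- Metformin and lifestyle are in both arms, so a higher background response could raise both rates.

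It can also be said that the outcomes named in the sample-size paragraph are mostly quantitative and will be compared by t or Mann-Whitney tests. That is true, but the plan states its power for proportions and compares qualitative variables by chi-square, so the stated figure has to be judged on that basis.

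What stands is that 30% has not been shown to be too low. None of this supplies a source for it or restores 80% power at 14 evaluable.

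**Conclusion.** The concern holds on two limited points. First, the citations, as the protocol describes them, do not give a 30% improvement proportion, so it is an unsupported assumption. Second, with 75% and 30% accepted, power is about 66–68% at the planned 14 evaluable per arm and 77–80% if nobody is lost, against a stated 80%.

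These figures assume a two-sided 5% test of one yes/no outcome. The 80% at 17 per arm is specific to the uncorrected chi-square, whose maximum type I error there is 5.8%; Fisher gives 68%.

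The powers of 18–58% at control rates of 40–56% are conditional on quadruple therapy staying at 75%. They show how sensitive the design is and do not predict this trial's power.

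**What to change.** In the Sample size paragraph:

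1. Call the 30% an assumption and remove the claim that [69-71, 73] give it.
2. Replace the 80% with about 66–68% power at 14 evaluable and 77–80% at 17 evaluable per arm, naming the test.
3. Add the sensitivity table for control rates from 25% to 56%. State that the end points come from other populations and outcomes, and that the low powers reflect a smaller assumed difference. Include the 85% versus 40% row to show this.

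In the statistical analysis section, report the between-group difference with its 95% confidence interval, so that a non-significant p-value is not left to stand alone.

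The cost is a rewritten paragraph, one table and a less favourable stated power. No extra patients are needed.

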## **STATISTIC ANALYSIS**

The data will be presented with descriptive statistics, mean and standard or median deviation and interquartile range, as well as percentages and incidence. For comparisons of numerical variables between the study groups, we will use Student's t if the distribution of the data follows a normal pattern, otherwise the Mann-whitney U test will be used; To compare qualitative variables we will use Chi square. Delta analysis will be performed for differences between groups. It will be considered significant when the value of p is  $<0.05$ . For the analysis and presentation of the data we will use the SPSS Version 15 and GraphPad Prism 5 programs.

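### The sample-size calculation rounds down, uses one arm's variance and under-allows for losses; after the planned 20% loss, power is about 70%, not 80%

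*Combined protocol and SAP*

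**What the plan says.** The Sample size paragraph of Material and Methods sizes the trial as a comparison of two proportions, "with a type I (alpha) error of 0.05 and a sample power of 80"%. The inputs are:

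- for quadruple therapy, "p1 = proportion of individuals in the best treatment who did not achieve improvement = 0.25"
- for metformin with lifestyle changes, the corresponding proportion p2, set at 0.70
- for the effect to be detected, "d = difference expected to be found = 0.45"
- an allocation ratio r of 1, and a squared multiplier (Z for alpha/2 plus Z for beta) of 7.9, so the calculation is two-sided.

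The displayed formula is n = 7.9 × p1(1 − p1)(r + 1) / (d² r). The paragraph ends: "n = 14 + 20% of losses = 17 patients per group".

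The Statistic Analysis section says of binary outcomes: "To compare qualitative variables we will use Chi square". It gives no method for missing data. This is the only power statement in the document.

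**The concern.** Each of three steps reduces the sample size. The formula's result appears to have been rounded down. The second proportion, 0.70, enters only through the difference d and never through the variance, so the answer depends on which arm is labelled p1. The loss allowance multiplies by 1.2, where keeping the target after a 20% loss requires division by 0.8.

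At stake is the stated 80%. If the trial is non-significant, readers will take it to have had a four-in-five chance of detecting a 45-point difference. If the true chance under the plan's own loss rate is nearer two-thirds to three-quarters, a negative result is weaker evidence than the protocol implies.

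**Working it through.** **Inputs**, all from the Sample size paragraph: non-improvement 0.25 and 0.70; d = 0.45, so d² = 0.2025; r = 1; multiplier 7.9 (7.849 unrounded); losses 20%. The variances are 0.25 × 0.75 = 0.1875 and 0.70 × 0.30 = 0.21, which sum to 0.3975. The mean proportion is 0.475.

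**1. The plan's own figure.** 7.9 × 0.1875 × 2 / 0.2025 = 14.63 (14.53 with 7.849). The printed 14 is this value rounded down; a minimum sample size rounds up, to 15. Then 14 × 1.2 = 16.8, printed as 17.

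**2. The variance term.**

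- Other arm in the same slot: 7.9 × 0.21 × 2 / 0.2025 = 16.39, so 17. Exchanging the labels changes the answer.
- Both arms, unpooled: 7.9 × 0.3975 / 0.2025 = 15.51, so 16.
- Pooled under the null, which corresponds to the chi-square: (1.96 × √(2 × 0.475 × 0.525) + 0.8416 × √0.3975)² / 0.2025 = 18.11, so 19.

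**3. The loss allowance.** 17 × 0.8 = 13.6 evaluable per arm, below even the plan's 14. Dividing instead gives 14 / 0.8 = 17.5 (18) and 15 / 0.8 = 18.75 (19).

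**4. Power at 75% versus 30%, two-sided 0.05.** The normal-approximation formulas are:

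- plan's formula: Φ(0.45 × √(n / 0.375) − 1.96), where 0.375 = 2 × 0.1875
- unpooled: Φ(0.45 × √(n / 0.3975) − 1.96)
- pooled: Φ((0.45 × √n − 1.96 × √(2 × 0.475 × 0.525)) / √0.3975)

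The exact Pearson figures come from enumerating every outcome of two binomials.

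| Evaluable per arm | Plan's one-variance formula | Unpooled normal | Pooled normal | Exact Pearson chi-square |
|---|---|---|---|---|
| 13 | 75.5% | 73.0% | 64.7% | 73.1% |
| 13.6 | 77.3% | 74.9% | 66.9% | n/a |
| 14 | 78.5% | 76.1% | 68.3% | 66.0% |
| 17 (no loss) | 85.8% | 83.7% | 77.3% | 79.9% |

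The exact chi-square is higher at 13 than at 14 because the test is discrete: its maximum type I error is 7.6% at 13 and 5.2% at 14. Averaging over random loss smooths this out. With 17 randomised per arm and independent binomial loss in each arm:

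| Loss | 0% | 5% | 10% | 15% | 20% |
|---|---|---|---|---|---|
| Exact Pearson power | 79.9% | 76.4% | 74.3% | 71.7% | 68.9% |

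More conservative tests do worse: Fisher's exact test and the Yates-corrected chi-square both give 57.4% at 13 and 51.7% at 14.

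**The case against.** The strongest objection is that these figures describe an analysis the protocol does not define. The Sample size paragraph names insulin resistance, islet function and cardiovascular function at 6 months. The Dependent Variables section defines these as quantitative, and the Statistic Analysis section would compare them by Student's t or Mann-Whitney. The one binary dependent variable is regression of hyperglycaemia and glucose intolerance at 12 months, which the sizing paragraph does not name. This stands as a limit: the figures apply to the 75% versus 30% scenario and say nothing about power for the continuous comparisons. It does not rescue the 80%, which the plan itself attaches to that scenario.

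Second, the shortfall depends mainly on losses. With none, 17 per arm gives 77.3% pooled, 79.9% exact Pearson and 83.7% unpooled, close to the stated figure. This is true, but the extra three patients were added to protect power against a 20% loss, and they do not. By the exact chi-square, a 5% loss already brings power to 76.4%.

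Third, rounding 14.63 to 14 is one patient, and 13.6 misses 14 by less than half a patient. On the plan's own formula the deficit after losses is only 1.5 to 2.7 points (78.5% at 14, 77.3% at 13.6). That also stands: the rounding is minor alone, and most of the gap comes from the variance term and the choice of test.

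Finally, no single range covers every method. The plan's formula lies above the 65–76% span of the pooled and unpooled approximations, and Fisher and Yates lie below it. The claim is therefore limited to the methods tried.

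**Conclusion.** The concern holds. The printed calculation is wrong in its rounding, its variance term and its loss allowance, and all three errors make n too small. In the plan's own scenario with its own 20% loss, 17 per arm gives roughly 70% power: 65–68% pooled, 73–76% unpooled, 68.9% by the exact Pearson chi-square averaged over random loss. The most favourable reading, the plan's own one-variance formula, gives 77.3% at 13.6 evaluable. None of the methods tried reaches "a sample power of 80"% after that loss.

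This rests on four assumptions: the responder proportions are 75% and 30%; the test is two-sided at 0.05; the uncorrected chi-square is used; and lost patients are not analysed, which is how the sizing paragraph treats them. If there were no losses, the chi-square would give about 77–80%.

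**What to change.** Keep 17 per arm and rewrite the Sample size paragraph. Name the formula, use both arms' proportions in the variance, round up, and allow for losses by dividing by (1 − 0.20). State the power that 17 per arm gives: roughly 70% after 20% losses (about two-thirds to three-quarters, depending on method), and about 77–80% by the chi-square with no losses.

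For reference only, the sizes for 80% power are:

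- Unpooled formula: 16 evaluable, 16 / 0.8 = 20 randomised per arm. The exact chi-square gives only 75.7% at 20 randomised with 20% random loss, so this size does not secure 80% for the planned test.
- Pooled formula, matching the chi-square: 19 evaluable, 19 / 0.8 = 23.75, so 24 randomised per arm. The exact chi-square gives 82.7% at 24 with the same loss.

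The cost is one paragraph of protocol text and a less favourable stated power. Enrolment, visits and tests are unchanged.
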